**11.0 Waiver of Consent/Authorization for Recruitment Purposes**

**This section is required when medical records may be reviewed to determine eligibility for recruitment.**

**11.1 \* PRACTICABILITY OF OBTAINING CONSENT PRIOR TO ACCESS: Study personnel need to access protected health information (PHI) during the recruitment process and it is not practicable to obtain informed consent until potential subjects have been identified: (REQUIRED)**

Yes

If **no**, a waiver of consent/authorization is NOT needed.

**11.2 \* RISK TO PRIVACY: A waiver for screening of health records to identify potential subjects poses no more than minimal risk to privacy for participants:**

Yes

If **no**, a waiver of authorization can NOT be granted.

**11.3 \* RIGHTS/WELFARE: Screening health records prior to obtaining consent will not adversely affect subjects' rights and welfare:**

Yes

If **no**, a waiver of authorization can NOT be granted.

**11.4 \* IDENTIFIERS: Check all the identifiers that will be collected prior to obtaining informed consent:**

Names  
 Dates  
 Postal addresses  
 Phone numbers  
 Fax numbers  
 Email addresses  
 Social Security Numbers\*  
 Medical record numbers  
 Health plan numbers

- Account numbers
- License or certificate numbers
- Vehicle ID numbers
- Device identifiers or serial numbers
- Web URLs
- IP address numbers
- Biometric identifiers
- Facial photos or other identifiable images
- Any other unique identifier
- None

Note: HIPAA rules require that you collect the minimum necessary.

**11.5 \* HEALTH INFORMATION: Describe any health information that will be collected prior to obtaining informed consent:**

No information will be collected prior to any form of consent.

To determine eligibility over the phone, information on MRI contraindications, general mental health, and physical health will be obtained to assess whether someone can complete the study. All information obtained before informed consent can be seen in the Eligibility Phone Screen, attached in Other Study Documents. All of the health information collected is necessary to determine eligibility. Because this information is collected prior to an in-person consent for eligibility purposes, a verbal consent will be obtained.

Note: HIPAA requires that you collect the minimum necessary.

**11.6 \* DATA RETENTION/DESTRUCTION PLAN: Describe your plan to destroy any identifiable data collected to determine eligibility for recruitment. This should be done at the earliest opportunity. If you plan to retain identifiable recruitment data, provide the justification for doing so:**

All data collected for eligibility purposes is collected via RedCap or Qualtrics and will remain electronic throughout the course of the study. While this data will not be used for analysis, it will be preserved as it is used to contact potential future participants (upon their consent to do so). All retained data collected is behind the secure UCSF firewall.

Subject identifiers will be kept separately from the research data in locked cabinets and locked office at the UCSF Osher Center.

Participant data will also be stored on VA servers at the Center for Imaging of Neurodegenerative Diseases at the San Francisco VA.

## 12.0 Risks and Benefits

**12.1 RESEARCH-RELATED RISKS: Check if your study involves any of these specific research-related risks to participants that may need to be disclosed in the consent form:**

- Physical discomforts or pain
- Risks to employment, or social or legal standing
- Risk that the study team may observe possible evidence of child abuse, elder abuse, or a threat to self or others that they are required to report

For reportable information, include details of the reporting plan below. (See

the Help link for Mandated Reporter child and elder abuse resources.)

\* For any boxes checked above, describe how you will minimize these risks and discomforts, e.g., adding or increasing the frequency of monitoring, additional screening to identify and exclude people with diminished kidney or liver function, or modification of procedures such as changing imaging studies to avoid giving contrast agent to people who are more likely to suffer side effects from it, etc.: **(REQUIRED)**

Data are password-protected and stored on secured UCSF PHI drive, only accessible on UCSF server. The computers will be checked regularly for proper and safe operation. Identifiable information is also stored as a hard copy in a locked office and locked file cabinet. Subjects will be carefully screened and subsequently informed about the fact that the principal investigator will be available at all times during the experiment. Subjects are informed that they may end the test session at any time and that participation in this research is voluntary.

Subjects are told that all information obtained is completely confidential and that their medical treatment at UCSF or the VA will not be affected, whether or not they choose to participate in this study. Coded numbers are assigned to each file in the data base to ensure patient privacy. To minimize the risk that sensitive subject information may be disclosed, all subject information will be kept in locked cabinets or in databases with secured passwords.

Records and data will be rigorously protected. Examiners will be clinically trained and sensitive to signs of stress, anxiety, or fatigue so that testing will be immediately terminated should any subject experience signs of discomfort. Any incidental findings regarding subjects' health will be submitted to his/her physician at subjects' request.

**Reportable information:** Evidence of elder or child abuse, as well as threat to self or others, will be reported. Participants are notified of this in the verbal and in-person consents. If it is suspected that the subject is in danger of harming him/herself or someone else, or if child abuse or neglect or elder abuse has occurred, appropriate authorities will be notified as required by law.

**Self-report measures:** The main risks associated with these procedures are fatigue and irritability with the testing procedure. The investigator and research assistants are trained to frequently check the subjects about their willingness and ability to continue with the testing. If the subjects express concerns about continuing with the testing, the investigator has instructed the research assistants to stop testing, offer a break, or, in case the subject is not willing to continue, to terminate the testing session. Overall, however, previous comparable studies have not resulted in any significant discomfort or anxiety expressed by the participating subjects.

**Risks associated with functional magnetic resonance imaging:** According to the FDA, there is currently no evidence that MRI with approved scanners of up to 7 Tesla signal strength are associated with adverse effects. moreover, other fMRI centers across the country are regularly using up to 7T MRI scanners for research purposes. However, there are two major sources of risk. First, the subject may experience discomfort being in the confined and sometimes noisy environment of the scanner. Second, the strong magnetic field will affect electronic, magnetic, and metal devices that subjects carry with them or that have been implanted in the subject's body. Additionally, female subjects capable of child-bearing, will be asked a number of questions regarding their use of reliable contraceptive methods in order to be as sure as possible that they are not pregnant. Even though there are no known risks to an unborn child associated with fMRI, women of child-bearing potential who are not using reliable contraceptive methods will be excluded from this study.

**Data collection:** The risks involve some degree of loss of privacy. This will be minimized as much as possible, as described elsewhere in this application.

**Yoga:** it is possible that yoga exercises can cause discomfort or pain. To minimize potential side effects exercises instructed over the internet (interactive Zoom), a second yoga instructor (CRC [name]) will observe the participants and correct as needed. Furthermore: a questionnaire for medical spine conditions that would require more individual attention and exercise modification will be used before the first yoga session. Thereby exercises, although taught in a group, can be partially individualized, and the risk of injury can be reduced.

## 12.2 \* RISKS: Describe any anticipated risks and discomforts not listed above: **(REQUIRED)**

See section 12.1.

12.3

**MINIMIZING RISKS:** Describe the steps you have taken to minimize the risks/discomforts to subjects. Examples include:

- designing the study to make use of procedures involving less risk when appropriate
- minimizing study procedures by taking advantage of clinical procedures conducted on the study participants
- mitigating risks by planning special monitoring or conducting supportive interventions for the study
- having a plan for evaluation and possible referral of subjects who report suicidal ideation

All risks and steps to minimize those risks are described in section 12.1 above.

12.5 \* **BENEFITS:** (REQUIRED) Note: These are the benefits that the IRB will consider during their review. They are not necessarily appropriate to include in the consent form.

Possible immediate and/or direct benefits to participants and society at large (check all that apply):

Positive health outcome (e.g. improvement of condition, relief of pain, increased mobility, etc.)

Closer follow-up than standard care may lead to improved outcomes or patient engagement

Health and lifestyle changes may occur as a result of participation

Knowledge may be gained about their health and health conditions

Feeling of contribution to knowledge in the health or social sciences field

The research presents a reasonable opportunity to further the understanding, prevention, or alleviation of a serious problem affecting the health or welfare of children

Other benefit (describe below)

None

12.6 **RISK TO BENEFIT RATIO:** Explain why the risks to subjects are reasonable in relation to anticipated benefits, if any, to the participant or society:

Chronic Pain is a serious problem, as discussed in section 7.0. Since the risks are relatively small, we believe the potential benefits to society outweigh the risks to the subjects.

12.7 \* **DATA AND SAFETY MONITORING:** Do you have a Data and Safety Monitoring Plan (DSMP) for this study (A DSMP is required for Greater than Minimal Risk research): (Click the Help link for guidance on risk determination) (REQUIRED)

Yes  No

**This is not required for minimal risk research but the UCSF IRB strongly recommends one to ensure the data collected are adequate to meet the research aims:**

13.0

## Data and Safety Monitoring Plan

13.1 \* **DATA AND SAFETY MONITORING PLAN (DSMP):** (REQUIRED) Provide a summary of the DSMP:

**All greater than minimal risk studies are required to provide a plan. Lack of an adequate plan is one of the most common reasons why IRB approval is delayed.**

**Instructions:**

Describe the plan for monitoring data quality and participant safety. Key areas that should be included in the plan are:

- An explanation of the plan to monitor data collection, study progress, and safety
- A description of who will perform the monitoring and at what frequency (e.g., the PI only, a contract research organization, a Data and Safety Monitoring Board or Data Monitoring Committee, etc.)
- The type of data and events that will be reviewed (e.g., adverse events, breaches of confidentiality, unanticipated problems involving risk to participants or others, unblinded efficacy data, etc.)
- Procedures and timeline for communicating monitoring results to the UCSF IRB, the study sponsor, and other appropriate entities

As appropriate:

- A plan for conducting and reporting interim analysis
- Clearly defined stopping rules
- Clearly defined rules for withdrawing participants from study interventions

Data and Safety Monitoring Plan (DSMP)

This DSMP was reviewed and accepted by NIH-NCCIH

Independent Monitoring Committee

**Feasibility Clinical Trial of Integrated Mind-Body Therapy for Chronic Low Back Pain  
(MBPR Study)**

**NIH Institute or Center:** National Center for Complementary and Integrative Health

**Grant Number:** R34AT010921-01A1

**Version Date:** 10/02/2020

**Version Number:** 1

# 1 STUDY OVERVIEW

## 1. Purpose of Study

The overall goal of this project is to developing a modified version of Mindfulness-Based Stress Reduction (MBSR) that we believe will prove to be more effective for chronic low back pain. Following the initial protocol development informed by a panel of international experts,  $4 \times 10 = 40$  participants will undergo 8-week Mindfulness-Based Pain Reduction (MBPR) classes that are iteratively improved through participant feedback. This study will enroll a total of 50 individuals with chronic low back pain, which includes a control group of 10 participants that will receive MBSR.

## 2. Adherence Statement

The Data Safety Monitoring Plan (DSMP) outlined below will adhere to the protocol approved by the UCSF IRB.

All protocol amendments, other than minor administrative changes as defined by the [NCCIH Guidance on Changes in Clinical Studies in Active Awards](#) will be submitted in a prospective manner to NCCIH except when necessary to protect the safety, rights, or welfare of subjects. IRB-approval will not be sought until after NCCIH approval of the protocol amendment has been obtained.

## 3 CONFIDENTIALITY

### 3.1 Protection of Subject Privacy

Subject confidentiality is strictly held in trust by the investigators, study staff, and the sponsor(s) and their agents. This study does not include testing of biological samples and genetic tests in addition to any study information relating to subjects.

The study monitor or other authorized representatives of the sponsor may inspect all study documents and records required to be maintained by the investigator, including but not limited to, medical records (office, clinic, or hospital) for the study subjects. The clinical study site will permit access to such records.

### 3.2 Confidentiality During Adverse Event (AE) Reporting

AE reports and annual summaries will not include subject or group-identifiable material. Each report will only include the identification code.

## 4 EXPECTED RISKS

- 4.1 Behavioral / Psychological Questionnaires:** These carry a minimal risk for emotional discomfort and stress.
- 4.2 Post-Intervention Interviews:** These carry a minimal risk for emotional discomfort and stress.
- 4.3 Privacy:** Participating in the study may result in a loss of privacy because the intervention is administered in a group setting. Participants will be asked not to share information related to other individuals when they are outside of class, but this cannot be guaranteed. Questionnaires will include background medical information and psychological scales and all research data will be stored on the secured web-based Research Electronic Data Capture (REDCap) and Qualtrics systems. Subjects are informed that they are free to refuse to participate in any stage of the work and can refuse to answer specific questions or questionnaire items if they wish.
- 4.4 Unexpected Events:** A physician is present or on call during all study procedures, and will be available if a participant experiences suicidal ideation or other mental health problem. All subjects will be provided with contact numbers in case distress arises following the experiment or intervention.

**4.5 Yoga-type movements and postures as a component of MBPR/MBSR:** Yoga has been found to be relatively safe in a number of large-scale randomized trials however any exercise program may result in muscle soreness or strains. Adverse events do occasionally occur and it is important that participants report any injuries to study staff. To improve safety, all participants will complete a pre-intervention assessment.

Prior to the start of MBPR/MBSR classes participants will be evaluated to determine if their pain worsens with flexion or extension. We will monitor pain levels during physical exercises. Classes are much smaller than common MBSR classes (10 participants instead of 15-25) and instructors are better able to help participants with individual adjustments and advice.

Finally, for those doing yoga-type exercises and postures, several minor adverse effects may occur and include increased low back pain intensity, muscle strain or sprain, or dizziness and are generally of short duration and alleviated by local physical measures (such as ice) and physical rest. They will be thoroughly addressed in the intervention.

**4.6 Fluctuations in Pain Levels:** Study physician [name] will weekly review the class reports and videos. He will be available by cell phone for more urgent problems between in-person consultations. Primary care physicians for each participant will receive information about the study before the participant begins the study. Study physician will help to make sure that primary care physicians are informed of any medical changes, and will consult with primary care physicians where indicated.

**4.7 MBPR and MBSR:** Similar interventions have been used with thousands of persons, including many with serious illness and pain conditions, and there have not been important adverse events reported to our knowledge. Participants can experience restlessness during the meditation practices or become aware of distressing emotions and traumatic memories. Our instructors are highly trained and experienced and will immediately inform the study physician, who will determine whether referral to behavioral medical care is warranted.

**4.8 Home Exercise Components:** Participants will be requested to do yoga-style exercises at home. Some people may experience initial discomfort when increasing their level of physical activity. There may also be a slight increase for physical risks when partaking in exercise activities. There are minor risks of injury during exercise, but these risks are minor and far out-weighed by the potential benefits of exercise.

**4.9 Audio/Video-Taping Instructors During Classes:** classes will be audio-videotaped to ensure intervention fidelity and provide feedback and troubleshooting for instructors. Some participants may experience a level of discomfort while being recorded during class. Although the recorders will be placed in front of the class to record the instructors' voice, there is a strong likelihood that some of the participants' movements and voices will be recorded. They may also feel that they are being monitored. Participants will be informed of the recording, and can sit farther from the microphone if they desire. Recordings will be kept on a HIPAA-compliant research network drive with password-restricted access limited to study staff. Recordings will be destroyed once the study is complete. Adverse event/unanticipated problems

## **5 ADVERSE EVENT/ UNANTICIPATED PROBLEMS**

### **5.1 Definitions**

#### **5.1.1 *Adverse Event (AE)***

An adverse event (AE) is any untoward medical occurrence in a subject during participation in the clinical study or with use of the experimental agent being studied. An adverse finding can include a sign or symptom, or any combination of these regardless of relationship to participation in the study.

#### **5.1.2 *Unanticipated Problems (UP)***

The Office for Human Research Protections (OHRP) considers unanticipated problems involving risks to subjects or others to include, in general, any incident, experience, or outcome that meets **all** of the following criteria:

- Unexpected in terms of nature, severity, or frequency given (a) the research procedures that are described in the protocol-related documents, such as the IRB-approved research protocol and informed consent document; and (b) the characteristics of the subject population being studied;
- Related or possibly related to participation in the research ("possibly related" means there is a reasonable possibility that the incident, experience, or outcome may have been caused by the procedures involved in the research); and
- Suggests that the research places subjects or others at a greater risk of harm (including physical, psychological, economic, or social harm) than was previously known or recognized.

### **5.1.3    *Serious Adverse Event (SAE)***

Serious adverse events (SAEs) are a subset of all Adverse Events (AEs). A serious adverse event (SAE) is one that meets one or more of the following criteria:

- Results in death
- Is life-threatening (places the subject at immediate risk of death from the event as it occurred)
- Results in inpatient hospitalization or prolongation of existing hospitalization
- Results in a persistent or significant disability or incapacity
- Results in a congenital anomaly or birth defect

An important medical event that may not result in death, be life threatening, or require hospitalization may be considered an SAE when, based upon appropriate medical judgment, the event may jeopardize the subject and may require medical or surgical intervention to prevent one of the outcomes listed in this definition.

## **5.2    Time Period and Frequency for Event Assessment and Follow-Up**

Unanticipated problems will be recorded in the data collection system throughout the study.

The PI will record all reportable events with start dates occurring any time after informed consent is obtained until 7 (for non-serious AEs) or 30 days (for SAEs) after the last day of study participation. At each study visit, the investigator will inquire about the occurrence of AE/SAEs since the last visit. Events will be followed for outcome information until resolution or stabilization.

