In addition, we will identify potentially eligible participants through review of our Medical Center's electronic medical records and send *letters inviting study participation using* the UCSF CTSI. Randomization for the final cohort will be performed using a computer-based assignment program, in which study staff must enter the participant ID number before randomization is revealed; assignment is then locked into the database. It will be stratified by sex, as responsiveness to mind-body interventions varies by sex. The UCSF study site of the ongoing NIH HEAL BACPAC initiative, for which both Drs [name] and [name] are key personnel, will create a large cohort of patients with cLBP (recruitment started June 2021), which can be approached for advertising our study.

MBPR will be delivered by an experienced mind-body practitioner with expert skills in mindfulness, MBSR and body awareness-enhancing approaches. Phase 1 includes a 2-day training retreat for the instructor led by [name] to prepare the MBSR instructor for the MBPR program. Home practice will be supported by audio recordings uploaded to the Insight Timer® smart phone platform. The Insight Timer application will also be used to track and record the frequency in which participants are doing a meditation practice in combination with a physical or electronic log. The instructor will use a workbook, audio recordings of guided meditation (these are standard recordings used e.g. in MBSR classes at the Los Angeles Insight Meditation Center), *Outsmart your Pain* by [name], PhD, a guide book for mindfulness with pain, and videos of yoga sequences (as outlined in handout, attached). Study participants will receive additional printed and audio support material.

**Schedule of Measures:** Participants will be assessed using computer-assisted questionnaires in the first and last week of the MBPR courses and will be followed up at 6 months for clinical outcomes. In addition we will use a mobile platform-based EMA, as detailed below.

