**10.14 TIME: What is the estimated time commitment for participants (per visit and in total):**

First round of questionnaires (at home): **~60 minutes**

Informed Consent Discussion (via phone): **~30 minutes**

The study will include up to 2 in-person visits at the San Francisco VA Medical Center for fMRI; all other visits are via zoom:

Visit 1 (fMRI) (at SFVAMC): **1 to 2 hours**

Initial check-in phone calls (phone or zoom) **~5-30 minutes each** depending on participant needs.

Visit 2 (MBPR Orientation Session; via zoom): **~2 hour**

Visit 3-10 (8 Classes MBPR Intervention; via zoom): **2 1/2 hours x 8**

Visit 11 (MBSR retreat day; via zoom): **6 hours**

Visit 12 (fMRI): **1 to 2 hours**

Second round of questionnaires (at home): **~60 minutes**

Potential Visit 5: qualitative interview: **~2 hours** (24 of the 50 participants)

Follow-up questionnaires at 6-months: **~60 minutes**

Total time involved with the study: **~ 33.6 to 38 hours over 9 - 10 weeks.**

The range is so wide, as it depends on the 2-hour exit interview (with 24 of the 50 participants).

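### Scheduled adverse event inquiry stops with the study visits at about week 8 to 10: none is specified for people who stop attending or at month 6, and the end of the recording window is undefined.

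*Protocol*

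**What the plan says.** **Inquiry.** DSMP section 5.2 states: "At each study visit, the investigator will inquire about the occurrence of AE/SAEs since the last visit". No other scheduled inquiry appears in the DSMP.

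**Recording window.** The same section records events from consent "until 7 (for non-serious AEs) or 30 days (for SAEs) after the last day of study participation". The last day of participation is not defined.

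**Visits.** Protocol section 10.14 numbers these visits: a first fMRI, an orientation, eight weekly Zoom classes (visits 3 to 10), a retreat day and a second fMRI. A qualitative interview is added for 24 of the 50 participants. The item "Follow-up questionnaires at 6-months" has a duration but no visit number. The section totals participation as "33.6 to 38 hours over 9 - 10 weeks".

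**Month 6.** Under Schedule of Measures in protocol section 7.9, participants "will be followed up at 6 months for clinical outcomes"; AEs are not mentioned. None of the 30 instruments in section 7.11 is described as an AE question. The content of the three qualitative items at 6 months is not given.

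**Home practice.** DSMP section 4.8 says: "Participants will be requested to do yoga-style exercises at home". Sections 4.5 to 4.8 name strain, increased back pain, dizziness, distressing emotions and traumatic memories among the expected risks.

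**The concern.** When inquiry is tied to attendance, people who leave the course are no longer asked. If some leave because of pain, injury or distress, their events are less likely to be counted than those of people who stay. Everyone moves to unprompted reporting once the course is over.

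The AE data have three uses: DSMP section 6.3 allows the study to be stopped for adverse effects, section 6.5 requires an annual check of AE rates against pre-study assumptions, and the study as a whole is meant to prepare a larger randomized trial. An under-count would make the programme look better tolerated than it is.

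The undefined end of participation adds a second problem. Two sites or two staff members could close the window months apart and both be following section 5.2.

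**Working it through.** **1. Is the contact list complete?** The durations in protocol section 10.14, in hours, taking one check-in call, can be added and compared with the stated total.

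- Minimum: first questionnaires 1 + consent 0.5 + fMRI 1 + check-in 5/60 + orientation 2 + classes 8 × 2.5 = 20 + retreat 6 + fMRI 1 + second questionnaires 1 + 6-month questionnaires 1 = 33.58.
- Maximum: 1 + 0.5 + 2 + 0.5 + 2 + 20 + 6 + 2 + 1 + interview 2 + 1 = 38.0.

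This reproduces the stated 33.6 to 38 hours. The budget therefore shows no unlisted contact after the course. One caveat is that check-in calls are listed in the plural, although they are labelled initial. The sum also shows that the hours include the 6-month questionnaire while being described as falling within 9 to 10 weeks.

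**2. How long is the stretch without scheduled inquiry?** The documents do not say whether 6 months runs from baseline or from the end of the 8-week course. Taking 6 months as 26 weeks:

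| Last visit | Month 6 from baseline (week 26) | Month 6 from course end (week 8 + 26 = 34) |
|---|---|---|
| Week 10 | 26 − 10 = 16 weeks | 34 − 10 = 24 weeks |
| Week 8 (no second fMRI, no interview) | 26 − 8 = 18 weeks | 34 − 8 = 26 weeks |

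The week 8 row applies to some participants, because protocol section 9.8 keeps people in the study who cannot have an MRI or are older than 65. Since month 6 has no listed AE item, the stretch does not clearly end there.

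**3. When does the recording window close?**

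- If participation ends at week 10, it closes at 10 + 1 = week 11 for non-serious AEs and at 10 + 30/7 = about week 14 for SAEs. Later events are outside the window, although outcome follow-up continues.
- If participation ends at month 6, the window stays open, but no inquiry is scheduled in it after the last visit.

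**4. How many people might leave?** DSMP section 6.2 plans for a 10% loss to follow-up: 0.10 × 50 = 5 participants.

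**5. What could that hide?** The documents give no AE risk for people who leave, so the risk p is an assumption. The chance of at least one AE among 5 leavers is 1 − (1 − p)^5:

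- p = 10%: 1 − 0.9^5 = 41%, expected 5 × 0.1 = 0.5 people
- p = 30%: 1 − 0.7^5 = 83%, expected 1.5
- p = 50%: 1 − 0.5^5 = 97%, expected 2.5

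These are upper bounds on what is missed, because other routes may catch some events.

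**The case against.** The best reply is that the plan captures AEs in more ways than section 5.2 suggests.

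- **Weekly classes are numbered visits.** Inquiry covers events since the last visit, so attendees are asked each week about the days between classes, including home exercise. A reader might infer that home-practice injuries go unasked. For attendees that is wrong.
- **Other routes exist.** Participants are told to report injuries and are given contact numbers (DSMP 4.4, 4.5). The study physician reviews class reports and videos weekly and liaises with primary care, and instructors escalate distress (4.6, 4.7). The SAP collects reasons for missed sessions and for dropout, and dropout reasons go into the annual report (6.5). These points stand. But class review sees only class events, and the rest depends on someone volunteering the information or on a reason for absence revealing an injury.
- **Symptom scales would show worsening.** PEG, PROMIS-29, PHQ-2 and GAD-2 would register worse pain or mood. They do not ask about injury, hospitalisation or care sought.
- **Section 7.11 is not a list of case report forms.** Forms and operating procedures are referred to separately and are not in the documents. An AE form at month 6 may exist. The supportable statement is that none is specified.
- **Later events may be outside the window by design.** This is a legitimate choice if participation ends at week 10, and the funder accepted the DSMP. It would settle the post-course period once written down. It does not settle the position of people who stop attending during the course.

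**Conclusion.** The point holds as a gap in specification. Active inquiry is tied to visits that end at about week 8 to 10. No inquiry is specified for non-attenders or at month 6, and the term that closes the 7- and 30-day windows is undefined. The post-course stretch is about 16 or 24 weeks after week 10, depending on where month 6 is counted from. Loss at the plan's 10% contingency would be about 5 of 50. AE counts may be too low; by how much is not known.

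Three stronger conclusions are tempting and not supported:

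- A reader might infer that harms are missed in those most likely to have been harmed. The documents give no AE risk by attendance, and someone who leaves the classes could still attend the second fMRI or return questionnaires. It is a plausible risk only.
- A reader might apply the figure of up to 20% poor adherence in DSMP section 6.1.2 and arrive at 10 of 50 people with little or no inquiry. Poor adherence is not non-attendance. Someone at half the classes is still asked about the whole interval at each one.
- A reader might infer that biased AE rates per class drive the stopping rule. Section 6.3 is qualitative, section 6.6 calls for aggregate safety tables, and no rate per class is specified.

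**What to change.** 1. Add a short structured AE/SAE item set to the 8-week and 6-month questionnaires: new or worse pain, injury, distress, medical care sought and hospitalisation since last contact. Send it to all enrolled participants, in both arms and in the single-arm cohorts, including those who stopped attending.
2. Ask the same items when the reason for dropout is collected, because people who leave may not return later questionnaires.
3. Reconcile DSMP section 5.2 with protocol section 10.14 by defining the last day of study participation, so that the recording window matches the follow-up actually done. State whether month 6 is counted from baseline or from the end of the course.

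The cost is a few items in questionnaires that are already sent, one or two sentences in the DSMP, about 1 to 2 more minutes per questionnaire, and more minor AEs to log. Responses from people who have left will still be incomplete, so reports should give the number asked alongside the number of events.
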